8.3 Radiology Studies

Central Radiology Review for Response: Patients who respond (CR, PR) to therapy or have long term stable disease (SD $>$ 6 months from study entry) on study will be centrally reviewed. Further, central review of disease progression will also occur. COG

Operations Center will notify the Imaging Center of any patient requiring central review. The Imaging Center will then request that the treating institution forward the requested images for central review. The central image evaluation results will be entered into RAVE for review by the COG Operations Center and for data analysis.

The images are to be forwarded electronically to the Imaging Research Center at Children's Hospital Los Angeles via the ImageInBox.

COG institutions that are not connected via the ImageInBox can send the images on CD ROM or USB flash drive. Submitted imaging studies should be clearly marked with the COG patient ID, study number (ADVL1217) and date and shipped to [name] at the address below:

[name], CRP
Administrator, Imaging Research Center
Children's Hospital Los Angeles
[name]
[name]
[contact]
[contact]
E-mail: [contact]

8.4 Pharmacology (Required)

8.4.1 Description of Studies and Assay

To date there is no experience with AZD1775 (MK-1775) in the pediatric population. To better characterize the pharmacokinetic (PK) properties of AZD1775 (MK-1775) in children, we will perform PK analyses on children treated on this study.

AZD1775 (MK-1775) will be measured in plasma using LC/MS/MS assay methodology and analyzed by Merck

8.4.2 Sampling Schedule-See Appx. V-B and Appx. VII for details

8.4.2.1 Blood samples will be obtained at the time points outlined in [Appendix VII](#).

8.4.3 Sample Collection and Handling Instructions

8.4.3.1 Blood samples (2-3 mL) will be collected in 4 ml K₂ EDTA (lavender-top) tubes, gently inverted 6 to 8 times, and immediately processed (See Section 8.4.4). Record the exact time that the sample is drawn along with the exact time that the drug is administered on the Pharmacokinetic Study Form (see [Appendix VII](#)).

If the blood samples cannot be centrifuged immediately, the tubes will be placed on ice. The total time from drawing blood to transferring the plasma to the freezer cannot exceed 30 minutes.

8.4.4 Sample Processing

THIS PROTOCOL IS FOR RESEARCH PURPOSES ONLY, SEE PAGE 1 FOR USAGE POLICY

See [Appendix XI](#) for processing details. Freeze immediately at -20 °C and store frozen until shipment. Complete the Pharmacokinetic Study Form (see [Appendix VII](#)), recording the date and time of collection for each sample. A copy of this form must accompany the sample(s) at time of shipment.

8.4.5 Sample Labeling

Each tube must be labeled with the COG patient ID and accession number, the study I.D. (ADVL1217), and the date and time the sample was drawn. Data should be recorded on the Pharmacokinetic Study Form (see [Appendix VII](#)), which must accompany the sample(s).

8.5 Pharmacodynamics (Required)

8.5.1 Description of Studies

We will assess the expression of p-CDC2, p-HH3 and γ -H2AX in peripheral blood mononuclear cells (PBMC) collected within 7 days prior to treatment start as well as at the time points listed in [Appendix VIII](#). Levels of γ -H2AX, p-CDC2 and p-HH3 expression will be assessed using flow cytometry.

γ -H2AX, p-CDC2 and p-HH3 measurement by flow cytometry:

Samples will be collected at each site using the Smart Tube kit (see [Appendix IX](#) for details). Once received at the laboratory of [name], samples will be thawed at 37°C for 30 seconds, and then washed with PBS. All subsequent steps will take place on ice. Samples will be blocked for one hour in Block-9 staining buffer (1g/l BSA, 8% mouse serum, 0.1g/l RNaseA, phosphate inhibitors, 0.25 g/l herring sperm DNA, 0.1% Triton X-100, 5mM EDTA, 0.05% NaN3, filtered through 0.22 μ m filter), and then incubated in 1:100 FITC-conjugated γ -H2AX/p-CDC2

and p-HH3 antibody. Additionally, the sample will be stained with 0.25ug/sample 7-Amino-Actinomycin D (7-AAD) (559925, BD Pharmigen) for the visualization of DNA content. Sample analysis will be performed by FACS Calibur flow cytometer (BD Biosciences), where data for about 20,000 total events will be collected. γ -H2AX levels will be visualized in FL1-H, and the DNA content in the FL3-H channel respectively.

Summary of assays to assess PD of AZD1775 (MK-1775) in PBMCs:

Molecular Feature	Assay (Reagent)
p-CDC2	R&D AF888
p-HH3	Cell Signaling #9701
γ -H2AX	Millipore 16-202A

PD analyses will be carried out in the laboratory of [name] upon validation of the p-CDC2 and p-HH3 assays.

Baseline expression of γ -H2AX, p-CDC2 and p-HH3 prior to AZD1775 (MK-1775) treatment will be established. We expect that expression of p-CDC2 will decrease and expression of γ -H2AX and p-HH3 increase after treatment with AZD1775 (MK-1775) and radiation. Since there might be physiologic variations in expression of these markers, we will obtain 2 baseline samples and calculate the intra-patient standard deviation of baseline levels. We will consider a change of 2 standard deviations as significant.

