8.5.2 Sampling Schedule

Two baseline samples will be collected before the first dose of AZD1775 (MK-1775). Every effort should be made to obtain the baseline (pre-treatment) samples on two different days, if feasible.

Blood samples will also be collected at the time points outlined in [Appendix VIII](#).

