11.5 Pharmacokinetic and Correlative Studies and Response Analysis

A descriptive analysis of pharmacokinetic (PK) parameters of AZD1775 (MK-1775) will be performed to define systemic exposure and other pharmacokinetic parameters. The PK parameters will be summarized with simple summary statistics, including means, medians, ranges, and standard deviations (if numbers and distribution permit).

Biologic activity of AZD1775 (MK-1775) will be explored using expression of p-CDC2, p-HH3 and γ -H2AX in PBMCs before and after administration of AZD1775 (MK-1775) using paired analysis methods.

While the primary aim of this study is to evaluate the toxicity of AZD1775 (MK-1775), patients will have disease evaluations performed as indicated in [Section 8.1](#). Disease response will be assessed according to criteria outlined in [Section 12.0](#), and will be reported descriptively. Progression-free survival and overall survival will also be summarized using the Kaplan-Meier method and including 95% confidence intervals. Both measurements of survival will be measured from the time of study entry.

All these analyses will be descriptive and exploratory and hypotheses generating in nature.

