APPENDIX VIII: PHARMACODYNAMIC STUDY FORM

COG Pt ID # _____ ACC # _____ **Day 1 of Protocol Therapy (XRT Start Date):** _____
Please do not write patient names on this form or on samples.

Body Surface Area: _____ m² Dose Level: _____ mg/m² Total Daily Dose: _____ mg

Blood samples will be obtained from all patients (1 ml per time point) prior to treatment start (two baseline samples are required) as well as at the following time points. Every effort should be made to obtain the baseline (pre-treatment) samples on two different days, if feasible. A total of 5 time points for the PD analysis will be collected.

Blood Sample No.	Time Point**	Scheduled Collection Time**	Actual Date Sample Collected	Actual Time Sample Collected (24-hr clock)
1*	Baseline/Pre-study	Within 7 days prior to XRT start date	/ /	_____ :____
2*	Baseline/ PD Day 1	Prior to Monday dose	/ /	_____ :____
AZD1775 (MK-1775) Dose on PD Day 1**		Date: ____ / ____ / ____	Time: ____ ____ : ____ ____	
3	PD Day 1	6-8 hr after Monday dose	/ /	_____ :____
AZD1775 (MK-1775) Dose on PD Day 5**		Date: ____ / ____ / ____	Time: ____ ____ : ____ ____	
4	PD Day 5	6-8 hr after Friday dose	/ /	_____ :____
5	PD Day 8	Prior to Monday dose	/ /	_____ :____
AZD1775 (MK-1775) Dose on PD Day 8**		Date: ____ / ____ / ____	Time: ____ ____ : ____ ____	

*Baseline samples should be taken at least 1 day apart, if feasible.

**Refer to [Appendix V-B](#) for PD collection based on XRT start date.

One copy of this Pharmacodynamic Study Form should be uploaded into RAVE. A second copy should be sent with the samples to the address listed in [Section 8.5.5](#). See [Section 8.5](#) for detailed guidelines for packaging and shipping PD samples.

Record any notes for Sample Storage Conditions below.

Notes:

If this form will be used as a source document, the site personnel who collected the samples must sign and date this form below:

Signature: _____
(site personnel who collected samples)

Date: _____

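### The 2-SD rule for pharmacodynamic change rests on two baseline samples per patient, so with no drug effect about 35% of comparisons per marker and time point would be called significant

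*Combined protocol and SAP*

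**What the plan says.** Section 8.5.1 covers three markers in peripheral blood mononuclear cells: p-CDC2, p-HH3 and γ-H2AX. Because the markers may vary physiologically, two baseline samples are to be taken in order to "calculate the intra-patient standard deviation of baseline levels. We will consider a change of 2 standard deviations as significant". The section expects p-CDC2 to fall and the other two to rise.

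Section 8.5.2 places both baseline samples before the first dose, on different days if feasible. Appendix VIII states: "A total of 5 time points for the PD analysis will be collected". Two of these are baselines, which leaves three post-dose samples: PD Day 1 at 6-8 hours, PD Day 5 at 6-8 hours, and PD Day 8 pre-dose.

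Section 11.5 says the markers will be explored "in PBMCs before and after administration of AZD1775 (MK-1775) using paired analysis methods" and describes all of these analyses as descriptive and exploratory. It neither repeats nor withdraws the 2-SD rule.

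The documents do not say whether change is measured from the baseline mean or from one baseline sample, whether the rule is one- or two-sided, whether the SD is pooled over patients, or how three markers at three time points are handled. They give no error rate for the rule.

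**The concern.** A 2-SD limit is a sensible screen when the SD and the reference level are well known. Here both come from the same two values in the same patient, so the limit is itself very noisy. If a patient's two baselines happen to agree, almost any later value exceeds it. If they happen to differ, a real change can be missed. The rule is meant to separate drug effect from physiologic variation, yet its threshold is set largely by chance.

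It is the only criterion in the documents for calling a pharmacodynamic change *significant*, and it serves secondary aims 1.2.2 and 1.2.3. Section 2.6 shows that marker modulation carries weight in this programme: it cites the adult dose needed to modulate p-CDC2 as part of the background to the higher dose levels. Per-patient calls that are mostly noise could be read as target engagement at any dose level.

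**Working it through.** The plan states no error rate for the rule, so there is no figure to reproduce. The rate is derived from the rule as written.

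**Inputs.** Two baselines per patient and a cut-off of 2 SD (Section 8.5.1); three post-dose samples per marker (Appendix VIII, 5 − 2 = 3); three markers (Section 8.5.1).

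**Assumptions.** No drug effect; independent normal values with within-patient SD σ; change measured from the mean of the two baselines; two-sided call.

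**Step 1, the SD.** With two values, S = |x₁ − x₂|/√2, on 1 degree of freedom. S/σ is distributed as |Z|, so P(S < 0.5σ) = P(|Z| < 0.5) = 38%. In more than a third of patients the 2-SD cut-off is therefore smaller than one true SD.

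**Step 2, the change.** Var(post − baseline mean) = σ²(1 + 1/2) = 1.5σ², independent of S. Hence (post − baseline mean)/(S√1.5) follows a t distribution with 1 degree of freedom.

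**Step 3, the false-positive rate.** P(|change| > 2S) = P(|t₁| > 2/√1.5) = P(|t₁| > 1.633) = 1 − (2/π)·arctan(1.633) = 0.3498. Simulation of 4 million patients gave 0.350. The result does not depend on σ. The conventional benchmark, with mean and SD known, is P(|Z| > 2) = 0.0455.

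**Step 4, other readings of the rule.**

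| Reading | Null rate per marker and time point |
|---|---|
| Change from baseline mean, two-sided | 35.0% |
| Change from a single baseline, two-sided | 37.7% |
| Baseline mean treated as known | 29.5% |
| SD with divisor n instead of n − 1 | 45.4% |
| Expected direction only, from baseline mean | 17.5% (nominal 2.3%) |
| Lognormal data, log-SD 0.3 to 1.0 | 34.6% to 34.9% |
| SD pooled over 6 / 12 / 26 / 77 patients, factor 2 kept | 15.4% / 12.8% / 11.5% / 10.7% |
| SD known exactly, factor 2 kept | 10.2% |

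The last row is 2·P(Z > 1.633). It is the floor for pooling when change is taken from the baseline mean; from a single baseline the floor is 2·P(Z > 1.414) = 15.7%.

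**Step 5, several looks per patient (by simulation, per-patient SD).** At least one false call over three time points for one marker: 54.4% two-sided, 33.7% in the expected direction. Over three markers, assuming they are independent: 1 − (1 − 0.544)³ = about 90% two-sided, and 1 − (1 − 0.337)³ = about 71% directional. Whatever the dependence between markers, the two-sided figure cannot fall below the single-marker 54%.

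**Step 6, scale of the problem.** Holding 5% two-sided with a per-patient SD from two samples would need a multiplier of 12.706 × √1.5 = 15.6 in place of 2.

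**The case against.** The strongest reply is that little depends on the rule. Section 11.5 calls these analyses exploratory. Escalation, de-escalation and the MTD rest on DLT counts (Sections 11.2 and 11.3), and escalation beyond the tabulated levels is to be considered on pharmacokinetics and toxicity (Section 5.3). Under the written rules a false pharmacodynamic call changes no dose. Section 11.5 already plans paired methods, so the group-level analysis need not use the 2-SD flag. The 5% benchmark is convention, not a figure in the plan. Because the markers have expected directions, 17.5% may be the fairer figure. The 90% needs an any-marker, any-time reading that the plan does not adopt, and it assumes independence between markers measured in the same blood draws.

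Most of this stands as a limit on consequence. It keeps the point to a reporting risk and off the list of threats to the primary aim. It does not rescue the rule. Exploratory status does not make *significant* an apt word for something that happens by chance in a third of comparisons. The paired methods are unspecified and do not replace the flag. Every reading examined is at least twice its nominal rate: 10.2% against 4.6% on the most favourable, 17.5% against 2.3% on the directional one.

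**Conclusion.** The concern holds. Read literally, the rule has a 35% false-positive rate per marker and time point, and 54% of patients would have at least one false call for a single marker across the three post-dose samples. These figures assume independent normal values with stable within-patient variability, a two-sided call, and change from the baseline mean. Per-patient two-sided alternatives range from 29.5% to 45.4%. The directional reading gives 17.5%, and pooling the SD without rescaling gives no less than 10.2%. The figure of about 90% over all nine marker-time combinations also requires independent markers and should be taken as illustrative.

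The rule should be changed before pharmacodynamic results are reported. The consequence is confined to a secondary, exploratory aim.

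**What to change.** Replace the 2-SD sentence in Section 8.5.1 and make Section 11.5 match:

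- For each marker, on the log scale, estimate one within-patient variance from all n patients with two valid baselines: s_w² = Σ(x₁ − x₂)²/(2n), on n degrees of freedom.
- Define change as the post-dose value minus the mean of the two baselines. Flag an individual change only if it exceeds t(0.975, n) × √1.5 × s_w in absolute value. The multiplier is 2.056 × 1.225 = 2.52 at n = 26 and 2.009 × 1.225 = 2.46 at n = 50; it is larger if fewer valid pairs are available.
- Make the main result the mean paired change with a 95% confidence interval by dose level, for each marker and time point, and treat individual flags as supporting description.
- State how the nine marker-time combinations are handled. The new cut-off holds about 5% for each one, not across all nine: if all nine were independent, 1 − 0.95⁹ = 37% of patients would still have at least one false flag. Naming one marker and time point in advance, or simply not interpreting any-of-nine, would deal with this.
- Define a valid baseline. For at least dose levels 3 to 7 with a Tuesday to Friday start, Appendix V-B schedules drug and radiation before the Monday PD Day 1 sample that Appendix VIII labels a baseline, while Section 8.5.2 requires both baselines before the first dose. These passages must be reconciled; a pair that includes a post-dose sample should not enter s_w.

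The cost is about a paragraph of analysis wording, with no new samples. The price is an assumption of common within-patient variability across patients, and fewer patients labelled as showing a change.

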8.5.2 Sampling Schedule

Two baseline samples will be collected before the first dose of AZD1775 (MK-1775). Every effort should be made to obtain the baseline (pre-treatment) samples on two different days, if feasible.

Blood samples will also be collected at the time points outlined in [Appendix VIII](#).

8.5.3 Sample Collection and Handling Instructions

Blood samples (1 ml per time point) will be collected in heparinized (green-top) tubes, transferred to a smart tube followed by a 30 minute incubation period in a 37°C water bath. For each time point a separate smart tube will be used. After the 37°C incubation period, the smart tubes will be activated and then incubated at room temperature for 8 minutes. Samples will be stored at -80°C until shipment. Record the exact time that the sample is drawn along with the exact time that the drug is administered. Transport of frozen vials, if necessary, should take place on dry ice. Please see details of preparation in [Appendix IX](#).

8.5.4 Sample Labeling

Each tube must be labeled with the COG patient ID and accession number, the study I.D. (ADVL1217), and the date and time the sample was drawn. Data should be recorded on the Correlative Study Form (see [Appendix VIII](#)), which must accompany the sample(s).

9.0 AGENT INFORMATION

9.1 AZD1775 (MK-1775)

NSC#751084;

[figure not shown]
9.1.1 Structure and molecular weight

Chemical name: 2-allyl-1-[6-(1-hydroxy-1-methylethyl)pyridin-2-yl]-6-{{[4-(4-methylpiperazin-1-yl)phenyl]amino}-1,2-dihydro-3H-pyrazolo[3,4-d]pyrimidin-3-one

Molecular formula: C₂₇H₃₂N₈O₂·0.5H₂O

Molecular weight: 500.6

Chemical Structure of AZD1775 (MK-1775):

9.1.2 Supplied by: Division of Cancer Treatment and Diagnosis (DCTD), NCI

9.1.3 Formulation

9.1.4 Storage

; dispense in the original container.

9.1.5 Administration

Patients will take AZD1775 (MK-1775) orally based on assigned dose. AZD1775 (MK-1775) will be administered orally once each day it is assigned directly after that day's radiation therapy fraction.

If a dose is vomited it should not be repeated; resume administration with the next regularly scheduled dose.

9.1.6 AZD1775 (MK-1775) Toxicities

The Comprehensive Adverse Events and Potential Risks list (CAEPR) provides a single list of reported and/or potential adverse events (AE) associated with an agent using a uniform presentation of events by body system. In addition to the comprehensive list, a subset, the Specific Protocol Exceptions to Expedited Reporting (SPEER), appears in a separate column and is identified with bold and italicized text. This subset of AEs (SPEER) is a list of events that are protocol specific exceptions to expedited reporting to NCI (except as noted below). Refer to the 'CTEP, NCI Guidelines: Adverse Event Reporting Requirements' http://ctep.cancer.gov/protocolDevelopment/electronic_applications/docs/aeguidelines.pdf for further clarification. Frequency is provided based on 213 patients. Below is the CAEPR for AZD1775 (MK-1775).

NOTE: Report AEs on the SPEER **ONLY IF** they exceed the grade noted in parentheses next to the AE in the SPEER. If this CAEPR is part of a combination protocol using multiple investigational agents and has an AE listed on different SPEERs, use the lower of the grades to determine if expedited reporting is required.

Version 2.5, April 18, 2018¹

¹This table will be updated as the toxicity profile of the agent is revised. Updates will be distributed to all Principal Investigators at the time of revision. The current version can be obtained by contacting [contact]. Your name, the name of the investigator, the protocol and the agent should be included in the e-mail.

²Infection includes all 75 sites of infection under the INFECTIONS AND INFESTATIONS SOC.

³Rash may include rash, erythema, eczema, and rash maculo-papular.

⁴Peripheral neuropathy includes both peripheral motor neuropathy and peripheral sensory neuropathy.

⁵Acute kidney injury includes renal impairment and acute renal insufficiency.

Adverse events reported on AZD1775 (MK-1775) trials but for which there is insufficient evidence to suggest that there was a reasonable possibility that AZD1775 (MK-1775) caused the adverse event:

BLOOD AND LYMPHATIC SYSTEM DISORDERS - Blood and lymphatic system disorders - Other (pancytopenia); Blood and lymphatic system disorders - Other (thrombocytosis); Febrile neutropenia; Leukocytosis

CARDIAC DISORDERS - Cardiac disorders - Other (cardiomegaly); Chest pain - cardiac; Myocardial infarction; Palpitations; Sinus bradycardia; Sinus tachycardia

EAR AND LABYRINTH DISORDERS - Ear pain; Hearing impaired; Tinnitus

EYE DISORDERS - Blurred vision; Cataract; Eye disorders - Other (eye swelling); Eye pain; Keratitis; Photophobia; Scleral disorder; Vision decreased; Watering eyes

GASTROINTESTINAL DISORDERS - Abdominal distension; Anal pain; Ascites; Belching; Bloating;

Cheilitis; Colitis; Dry mouth; Duodenal ulcer; Dysphagia; Enterocolitis; Flatulence; Gastric ulcer; Gastritis; Hemorrhoids; Lower gastrointestinal hemorrhage; Oral pain; Rectal hemorrhage; Rectal pain; Small intestinal obstruction

GENERAL DISORDERS AND ADMINISTRATION SITE CONDITIONS - Chills; Death NOS; Edema trunk; Flu like symptoms; Gait disturbance; General disorders and administration site conditions - Other (catheter site pain); Infusion site extravasation; Malaise; Non-cardiac chest pain; Pain

IMMUNE SYSTEM DISORDERS - Allergic reaction; Anaphylaxis; Cytokine release syndrome

INJURY, POISONING AND PROCEDURAL COMPLICATIONS - Fall; Injury, poisoning and procedural complications - Other (excoriation); Injury, poisoning and procedural complications - Other (ligament sprain)

INVESTIGATIONS - Alkaline phosphatase increased; Aspartate aminotransferase increased; Blood bilirubin increased; Creatinine increased; Electrocardiogram QT corrected interval prolonged; GGT increased; Investigations - Other (blood urea increased); Lymphocyte count increased; Weight loss

METABOLISM AND NUTRITION DISORDERS - Alkalosis; Hypercalcemia; Hyperglycemia; Hyperkalemia; Hyperuricemia; Hypoalbuminemia; Hypocalcemia; Hyponatremia; Hypophosphatemia; Tumor lysis syndrome

MUSCULOSKELETAL AND CONNECTIVE TISSUE DISORDERS - Arthralgia; Arthritis; Bone pain; Flank pain; Generalized muscle weakness; Muscle cramp; Muscle weakness lower limb; Musculoskeletal and connective tissue disorder - Other (groin pain); Neck pain; Pain in extremity

NEOPLASMS BENIGN, MALIGNANT AND UNSPECIFIED (INCL CYSTS AND POLYPS) - Neoplasms benign, malignant and unspecified (incl cysts and polyps) - Other (carcinoid tumor); Tumor pain

NERVOUS SYSTEM DISORDERS - Central nervous system necrosis; Cognitive disturbance; Dysesthesia; Encephalopathy; Lethargy; Nervous system disorders - Other (hemiparesis); Paresthesia; Peripheral neuropathy⁴; Presyncope; Somnolence; Syncope

PSYCHIATRIC DISORDERS - Agitation; Anxiety; Confusion; Depression

RENAL AND URINARY DISORDERS - Acute kidney injury⁵; Hematuria; Urinary frequency; Urinary incontinence; Urinary retention; Urinary tract pain

REPRODUCTIVE SYSTEM AND BREAST DISORDERS - Genital edema; Reproductive system and breast disorders - Other (female genital tract fistula)

RESPIRATORY, THORACIC AND MEDIASTINAL DISORDERS - Allergic rhinitis; Bronchopulmonary hemorrhage; Epistaxis; Hiccups; Nasal congestion; Pleural effusion; Pneumonitis; Pulmonary hypertension; Respiratory, thoracic and mediastinal disorders - Other (diaphragmalgia); Voice alteration; Wheezing

SKIN AND SUBCUTANEOUS TISSUE DISORDERS - Alopecia; Bullous dermatitis; Dry skin; Hyperhidrosis; Pain of skin; Palmar-plantar erythrodysesthesia syndrome; Pruritus; Purpura; Rash aereiform; Skin ulceration; Urticaria

VESTIBULAR DISORDERS - Flushing; Hematoma; Hot flashes; Hypertension; Hypotension; Thromboembolic event

Note: AZD1775 (MK-1775) in combination with other agents could cause an exacerbation of any adverse event currently known to be caused by the other agent, or the combination may result in events never previously associated with either agent.

